## **12.0 PUBLICATION OF STUDY RESULTS**

No publication or disclosure of study results will be permitted, except under the terms and conditions of a separate, written agreement between Investigator-Sponsor and the Investigator and/or the Investigator's institution. The Investigator-Sponsor will have the opportunity to review and approve all proposed abstracts, manuscripts, or presentations regarding this study

USRC Kidney Research  
Original Version 5.0  
28JUL2022  
Protocol No USRC-2021-002

prior to submission for publication/presentation. Any information identified by the Investigator-Sponsor as confidential will be deleted prior to submission.

For all publications relating to the study, the institution will comply with recognized ethical standards concerning publications and authorship, including: Section II - "Ethical Considerations in the Conduct and Reporting of Research" of the Uniform Requirements for Manuscripts Submitted to Biomedical Journals, <http://www.icmje.org/index.html#authorship>, established by the International Committee of Medical Journal Editors.

## 1. ABBREVIATIONS

Abbreviation or Term	Definition
AE	Adverse event
AESI	Adverse event of special interest
ASCVD	Atherosclerotic cardiovascular disease
CHF	Congestive heart failure
CKD	Chronic kidney disease
eGFR	Estimated Glomerular Filtration Rate
EOT	End of treatment
ESA	Erythropoiesis-stimulating agent
IV	Intravenous
KFRE	Kidney Failure Risk Equation
MedDRA	Medical Dictionary for Regulatory Activities
PP	Per protocol
PT	Preferred term
RBC	Red blood cell
SAE	Serious adverse event
SOC	Standard of care

Abbreviation or Term	Definition
TSAT	Transferrin saturation

## 2. INTRODUCTION

This statistical analysis plan (SAP) contains definitions of analysis sets and statistical methods for the planned analyses in protocol USRC-2021-002 (Version 5.0, 28JUL2022).

### 2.1. Overview of Trial Design

This is an investigator-initiated multicenter, randomized, double-blind, placebo-controlled, pragmatic clinical trial in patients with advanced chronic kidney disease (CKD) to determine the effect of ferric citrate versus placebo on the time to a composite endpoint of initiation of maintenance dialysis or all-cause mortality. Secondary objectives of this trial are to evaluate the impact of ferric citrate on time to all-cause hospitalization and individual components of the primary endpoint.

The study periods are:

- Screening Period: Up to 45 days prior to Day 1. Standard of Care (SOC) laboratory collection permitted up to 45 days (up to 90 days for estimated glomerular filtration rate [eGFR]) prior to Day 1.
- Treatment Period: Up to 9 months
- Safety follow-up Period: 30 days after end of treatment (EOT)

Subjects will be stratified by site and by eGFR (above or equal to/below 15 ml/min/1.73m^2) randomized in a 1:1 ratio to receive either ferric citrate or matching placebo.

All subjects will receive a fixed dose of two tablets orally taken with meals or snacks up to three times per day. The maximum daily dose is six tablets. Subjects will remain on study drug for up to 9 months followed by an additional 30-day safety follow-up period. Study drug will be stopped for subjects who initiate maintenance dialysis or receive a kidney transplant. Subjects who undergo maintenance dialysis or receive a kidney transplant will be removed from study with no follow-up visit, however, these subjects will have a vital status check (to ascertain mortality) performed 30-days following the relevant event.

Each randomized subject will complete five study visits (2 in-person and three phone/virtual or in-person). Study visits during the treatment period will be conducted as part of routine scheduled clinical encounters. Standard of care local laboratory results will be collected, including the monitoring of phosphorus and iron indices (TSAT and ferritin) at quarterly intervals.

Management of serum phosphorus and iron sufficiency will be directed at the discretion of the treating physician and/or Investigator independent of study drug with the exception of protocol required safety adjustments of study drug. There is no minimum allowable dose of study drug, and the prescribed dose of study drug will be adjusted only in the event of a safety or tolerability concern.

### 3. STATISTICAL CONSIDERATIONS

Data collected throughout the study will be summarized in tables with descriptive statistics and listed in by-subject listings. Missing information will be summarized by counts for each variable. Continuous variables will be summarized using number of subjects with data, mean, standard deviation, median, first and third quartile, minimum, and maximum. For categorical variables, the number and percentage of subjects in each category will be tabulated. Summaries will be provided by treatment group within appropriate analysis populations and by time point/time period, as appropriate.

#### 3.1. Sample Size

The sample size for this study is driven by the primary endpoint, initiation of maintenance dialysis or all-cause mortality and is based on the observed data from the pilot study (Block, 2019) using nearly identical inclusion and exclusion criteria. The observed rate of the primary composite endpoint in the pilot study (all-cause mortality, maintenance dialysis or kidney transplant) for patients in the standard of care arm was 0.94 events per person-year of follow up. The observed hazard ratio was 0.42 (58% relative risk reduction,  $p=0.002$ ) for the primary composite endpoint when comparing ferric citrate treated patients versus usual care.

Assuming 1 year recruitment and 0.75 years of follow up (9 months) for each individual and a hazard ratio of 0.60 (40% relative risk reduction), a sample size of 400 patients (200 per arm) provides 90% power with a 2-sided alpha  $p < 0.05$ . Assuming a hazard ratio of 0.50 (50% relative risk reduction), a sample size of 225 patients provides 90% power with a 2-sided alpha  $p < 0.05$ .

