## 1.0 PROTOCOL SUMMARY

### 1.1 Synopsis

[figure not shown]
| Protocol Synopsis                    |   |
|--------------------------------------|---|
| Protocol Title                       | Ferric Citrate for the Prevention of Renal Failure in Adults with Advanced Chronic Kidney Disease (FRONTIER)  |
| Protocol Number                      | USRC-2021-002   |
| Investigational Product              | Auryxia (Ferric Citrate-KRX-0502)   |
| Reference Therapy, as applicable     | Matching Placebo  |
| Study Population                     | The study population will consist of adult subjects $\geq 18$ years old with a diagnosis of non-dialysis dependent (NDD) advanced chronic kidney disease (CKD)  |
| Number of Study Sites                | Multicenter, up to 25 sites in the United States (US)   |
| Planned Number of Subjects           | Up to 400 subjects will be randomized 1:1 to receive either ferric citrate or matching placebo  |
| Primary Objective/Endpoint           | To determine the effect of ferric citrate on the time to a composite endpoint of initiation of maintenance dialysis or all-cause mortality compared to placebo in adult patients with advanced CKD.   |
| Secondary Objectives/Endpoints       | 

Time to first hospitalization event reported as a serious adverse event (SAE) (excluding disease-related hospitalization [e.g., dialysis access placement, dialysis initiation, kidney transplant] and elective procedures)

Component of Primary – Time to Initiation of Maintenance Dialysis

Component of Primary – Time to All-Cause Mortality

  |

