| 
Statistical considerations
 

a. General analysis plan

b. Rationale for number of subjects

 | 
The primary endpoint is the time to a composite endpoint of initiation of maintenance dialysis or all-cause mortality. The primary endpoint will be analyzed by Cox-proportional hazards regression model. Hazards ratios and corresponding 95% confidence intervals will be presented.
 
The sample size for this study is driven by the primary endpoint, initiation of maintenance dialysis or all-cause mortality and is based on the observed data from the pilot study using nearly identical inclusion and exclusion criteria. The observed rate of the primary composite endpoint in the pilot study (all-cause mortality, maintenance dialysis or kidney transplant) for patients in the standard of care arm was 0.94 events per person-year of follow up. The observed hazard ratio was 0.42 (58% relative risk reduction, <math>p=0.002</math>) for the primary composite endpoint when comparing ferric citrate treated patients versus usual care.
 
Assuming 1 year recruitment and 0.75 years of follow up (9 months) for each individual and a hazard ratio of 0.60 (40% relative risk reduction), a sample size of 400 patients (200 per arm) provides 90% power with a 2-sided alpha <math>p <0.05</math>. Assuming a hazard ratio of 0.50 (50% relative risk reduction), a sample size of 225 patients provides 90% power with a 2-sided alpha <math>p <0.05</math>.
 |
|--|---|

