F: Both height and weight will be collected at the Day 1 visit. Height may be self-reported. Weight only will be collected during the treatment period and may be captured using data from the clinical encounter.

G: Serum or urine pregnancy test (women of childbearing potential) must be done at any point within 30 days of Day 1. Can be performed on Day 1 if prior to any Day 1 procedures. Results must be available prior to the 1st dose of study drug.

H: Other laboratory assessments include urine chemistry, hepatic panel, magnesium, cystatin-C and PTH if available (section 9.4, Table 2).

I: The most recent laboratory assessments prior to EOT will be utilized

J: Routine concomitant medications will be assessed at each in-person visit (Screening, Day 1, Month 9). Concomitant medications of interest will be assessed at Screening at then at each subsequent study visit (see Section 9.5.1).

K: Targeted medical history (refer to section 9.2.1)

L: Collection begins at initiation of study drug treatment (1st dose of study drug) and continues through the follow-up visit. Refer to Section 9.5.2.

M: Prescription for study drug must be sent to USRC Rx Pharmacy for processing at time of randomization to ensure on-time delivery prior to Day 1. Refill prescriptions or changes to prescription will be sent to the pharmacy as needed. Dispensing will be a minimum of 3 months supply.

N: Collection begins at initiation of study drug treatment (1st dose of study drug) and continues through the follow-up visit. Refer to Section 9.5.2.

O: Endpoint assessment includes initiation of dialysis, vital status (alive or deceased), transplant, and hospitalization. Any subject who either receives a kidney transplant or initiates maintenance dialysis, and has not withdrawn consent from study participation, will have a vital status check performed at 30-days following the relevant event.

P: If there are delays related to shipment from the USRC Rx pharmacy, study drug will be provided to subjects within 12 days of the Day 1 visit.

Q: Study drug accountability is performed at in-person visits only.

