## **4.2 Study Endpoints**

### **4.2.1 Primary Endpoint**

Time to a composite endpoint of initiation of maintenance dialysis or all-cause mortality

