### **10.1 Sample Size Determination**

The sample size for this study is driven by the primary endpoint, initiation of maintenance dialysis or all-cause mortality and is based on the observed data from the pilot study using nearly identical inclusion and exclusion criteria. The observed rate of the primary composite endpoint in the pilot study (all-cause mortality, maintenance dialysis or kidney transplant) for patients in the standard of care arm was 0.94 events per person-year of follow up. The observed hazard ratio was 0.42 (58% relative risk reduction,  $p=0.002$ ) for the primary composite endpoint when comparing ferric citrate treated patients versus usual care.

Assuming 1 year recruitment and 0.75 years of follow up (9 months) for each individual and a hazard ratio of 0.60 (40% relative risk reduction), a sample size of 400 patients (200 per arm)

provides 90% power with a 2-sided alpha  $p < 0.05$ . Assuming a hazard ratio of 0.50 (50% relative risk reduction), a sample size of 225 patients provides 90% power with a 2-sided alpha  $p < 0.05$ .

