### 3.3. Missing or Incorrect Data

Discontinuation from study intervention is different from discontinuation from the study, and remaining study procedures will be completed as indicated by the study protocol unless the subject withdraws consent for participation in the study. The date of vital status for all patients who early term will be capped at 37 days post the early termination date. For all patients who complete the study through 9 months, the 10-month follow-up safety visit date will be capped at 307 days post study drug Day 1.

All data pertaining to the primary and secondary endpoints collected at any point during the study, both during study drug treatment and post-study drug treatment discontinuation, will be used for the primary analysis of the endpoints and its individual components.

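### The 90% power for dialysis or death uses a pilot control rate, 0.94 per person-year, that also counts kidney transplant

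*SAP*

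**What the plan says.** Protocol 4.2.1 defines the primary endpoint as "Time to a composite endpoint of initiation of maintenance dialysis or all-cause mortality". Protocol 10.1, SAP 3.1 and the synopsis say that this endpoint drives the sample size.

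The same paragraphs take the control rate from the pilot. SAP 3.1 introduces it as "The observed rate of the primary composite endpoint in the pilot study (all-cause mortality, maintenance dialysis or kidney transplant"), and Protocol 10.1 gives its value "for patients in the standard of care arm was 0.94 events per person-year of follow up". With 0.75 years of follow-up per person and a hazard ratio of 0.60, the conclusion is that "a sample size of 400 patients (200 per arm) provides 90% power". A second case, at a hazard ratio of 0.50, says that "a sample size of 225 patients provides 90% power with a 2-sided alpha". The synopsis sets the planned size: "Up to 400 subjects will be randomized 1:1 to receive either ferric citrate or matching placebo".

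Neither document gives the transplant share of the 0.94, a rate without transplants, a drop-out rate or the sample-size formula.

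Transplant is recorded in this trial (Protocol Table 1, note O: "Endpoint assessment includes initiation of dialysis, vital status (alive or deceased), transplant, and hospitalization"), but it is not part of the primary endpoint. Under Protocol 5.1 and SAP 2.1 a transplanted subject leaves the study, with one check of vital status 30 days later.

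**The concern.** The control rate and the tested endpoint do not match. A transplant that counted as an event in the pilot rate is, in this trial, an exit that removes time at risk for dialysis. Using 0.94 unadjusted can only overstate the expected number of primary events, or leave it unchanged if the pilot control arm had no transplants as first events.

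This power statement is the only justification given for up to 400 subjects. Anyone reading a null or borderline result will want the power for the endpoint that was tested, and the plan does not supply the rate needed to work it out.

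**Working it through.** **Inputs from the documents.** Control rate 0.94 per person-year; hazard ratio (HR) 0.60; 200 per arm; T = 0.75 years; two-sided alpha 0.05; target power 90% (Protocol 10.1, SAP 3.1). For a longer horizon, SAP 3.3 caps the Month 10 visit at Day 307, so T = 307/365.25 = 0.841 years.

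**Inputs assumed, because the documents give neither.** s = share of pilot control events that were transplants; d = proportion lost by 0.75 years.

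**Step 1: reproduce the plan's figure (s = 0, d = 0, exponential survival).**

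- Control risk: 1 − exp(−0.94 × 0.75) = 50.6%. Treated risk: 1 − exp(−0.564 × 0.75) = 34.5%.
- Expected events: D = 200 × (0.5059 + 0.3449) = 170.2.
- Schoenfeld: events needed 4(1.96 + 1.2816)²/ln(0.60)² = 161.1, N = 381. Power = Φ(√D/2 × |ln HR| − 1.96) = Φ(3.332 − 1.96) = 91.5%.
- Freedman: 169 events needed, N = 398. Power = Φ(√D × (1 − HR)/(1 + HR) − 1.96) = Φ(3.261 − 1.96) = 90.3%.
- A comparison of two proportions needs 197 per arm, 394 in total.

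So 400 is a correct answer to the stated inputs, with 2 to 19 subjects to spare by the two survival formulas.

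**Step 2: move to the tested endpoint.** The control hazard of dialysis or death is 0.94(1 − s), and the treated hazard is HR times that. The exit hazard in both arms is c = 0.94s − ln(1 − d)/0.75. Event probability = h/(h + c) × (1 − exp(−(h + c)T)).

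Example with s = 10%, d = 10%, T = 0.75:

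- h = 0.846 and 0.508; c = 0.094 + 0.1405 = 0.2345.
- Event probabilities are 43.5% and 29.2%, giving 145.3 events.
- Schoenfeld: Φ(3.079 − 1.96) = 86.8%. Freedman: Φ(3.014 − 1.96) = 85.4%.

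Power at N = 400, HR 0.60 (Schoenfeld / Freedman):

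| Transplant share | Drop-out | Events, 0.75 y | Power, 0.75 y | Events, Day 307 | Power, Day 307 |
|---|---|---|---|---|---|
| 0% | 0% | 170.2 | 91.5 / 90.3 | 184.7 | 93.5 / 92.5 |
| 0% | 10% | 162.3 | 90.2 / 89.0 | 175.4 | 92.3 / 91.2 |
| 5% | 0% | 161.2 | 90.0 / 88.8 | 175.0 | 92.2 / 91.1 |
| 10% | 0% | 152.3 | 88.3 / 87.0 | 165.3 | 90.7 / 89.5 |
| 10% | 10% | 145.3 | 86.8 / 85.4 | 156.9 | 89.2 / 87.9 |

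**Step 3: break-even share for 90% with no drop-out.** At 0.75 years it is 1.1% (Freedman) or 5.1% (Schoenfeld). At Day 307 it is 8.5% or 12.2%. If the rate is lowered but no transplant exits are modelled, the limits at 0.75 years are 1.6% and 7.1%, that is, rates of 0.925 and 0.873.

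**Step 4: the other cases.** N = 225 at HR 0.50 has less slack: 90.9% (Schoenfeld) or 88.7% (Freedman) at 0.75 years with no loss. N = 400 at HR 0.50 has ample slack: 99.2% with no loss and 98.2% at 10% plus 10% (Schoenfeld, 0.75 years).

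**The case against.** The strongest reply is that no failure of power is shown. The calculation is right, the text openly names the transplant component, and both loss inputs are assumed. All of that stands.

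The design hazard ratio of 0.60 is also a planning choice, milder than the pilot's 0.42. At a hazard ratio of 0.55, power in the 10% plus 10% case over 0.75 years is still 94.4% (Schoenfeld) or 93.2% (Freedman). That is a real margin, but on effect size. It does not make 90% at 0.60 correct for an endpoint whose rate is not given.

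Follow-up may also run beyond nine months. SAP 3.3 brings in "All data pertaining to the primary and secondary endpoints collected at any point during the study", and endpoints are assessed at Month 10. On that reading 0.75 years is conservative, and the extra time offsets part of the loss. The horizon therefore works in the plan's favour, although neither SAP 3.1 nor SAP 3.4.4 says which applies.

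Several provisions limit losses: exclusion 13 (scheduled living-donor transplants), record-based tracing of subjects lost to follow-up (Protocol 8.3) and optional replacement of undosed subjects (Protocol 5.1.1). A reader might also infer that nothing was allowed for drop-out. The documents state no allowance, but 400 against Schoenfeld's 381 leaves some room, so its absence is not established. The missing drop-out rate and horizon are gaps in detail that bear on how the power is restated. They are not separate faults.

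**Conclusion.** The point holds as a mismatch in one input: the control rate belongs to a three-part composite, and the power is claimed for two of its parts. Over assumed transplant shares and drop-out of 0 to 10% each, the loss against the no-loss figure is 0 to about 5 percentage points, for example 91.5% to 86.8% (Schoenfeld) or 90.3% to 85.4% (Freedman) at 0.75 years.

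Three stronger readings are not supported:

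- **That the trial is underpowered.** The transplant share and drop-out are unknown, and the shortfall may be negligible.
- **That the sample size was miscalculated.** It reproduces from its inputs.
- **That the whole power figure belongs to another endpoint.** Only the control rate is borrowed; the 0.60 was chosen.

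The results rest on exponential survival, equal transplant and drop-out hazards in both arms, and the same hazard ratio for the two-part endpoint. The break-evens depend on a formula that the plan does not name. The 0.94 comes from one arm of a 200-subject pilot and has no interval, so they are approximate. The point matters near a hazard ratio of 0.60 and hardly at all for N = 400 at 0.50.

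**What to change.** In SAP 3.1, Protocol 10.1 and the synopsis:

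- Replace 0.94 with the pilot control-arm rate for dialysis or death, with transplant treated as a censoring exit.
- Restate the power at N = 400 and hazard ratio 0.60, and at N = 225 and 0.50 if that case is kept.
- Name the formula, the drop-out assumption and the follow-up horizon used.

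The cost is one recalculation and matching wording in three places, with no change to enrolment. Protocol 5.2 reports the pilot's dialysis result separately from its composite, which suggests that component events were recorded, but the needed rate is not in these documents. If it cannot be obtained, give the power over a stated range of transplant shares. The downside is that the stated power may become slightly less favourable.

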### 3.2. Populations for Analyses

The following analysis populations will be used in this study:

- Randomized population: defined as all randomized subjects.
- Full analysis population: defined as randomized subjects receiving one or more doses of study drug. This population will be analyzed based upon the randomized treatment.
- Safety population: defined as all subjects who received at least one dose of study drug. This population will be analyzed based upon the actual treatment received.
- Per protocol (PP) population: defined as full analysis subjects who received a non-zero dose of study medication at least 70% of their time in study and have no protocol deviations affecting the primary endpoint analyses. This population will be analyzed based upon the treatment received.

Any subject who is randomized to study intervention but does not receive study drug will be considered an early termination.

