## **5.0 STUDY DESIGN**

### **5.1 Overall Design**

This is an investigator-initiated multicenter, randomized, double-blind, placebo-controlled, pragmatic clinical trial in patients with advanced CKD to determine the effect of ferric citrate versus matching placebo on the time to a composite endpoint of maintenance dialysis or all-cause mortality.

Subjects who meet all inclusion and none of the exclusion criteria will be randomized in a 1:1 ratio (stratified by site and eGFR) to receive either ferric citrate or matching placebo. All subjects will receive a fixed dose of 2 tablets orally taken with meals or snacks up to 3 times per day. The maximum daily dose is 6 tablets/day. Subjects will remain on study drug for up to 9 months followed by an additional 30-day safety follow-up period. Study drug will be stopped for subjects who initiate maintenance dialysis or receive a kidney transplant. Subjects who undergo maintenance dialysis or receive a kidney transplant will be removed from study with no follow-up visit, however, these subjects will have a vital status check (to ascertain mortality) performed at 30-days following the relevant event.

The study periods are:

- Screening Period: Up to 45 days prior to Day 1. Standard of Care (SOC) laboratory collection permitted up to 45 days (up to 90 days for eGFR) prior to Day 1.
- Treatment Period: Up to 9 months
- Safety follow-up Period: 30 days after EOT

Each randomized subject will complete 5 study visits (2 in-person and 3 phone/virtual or in-person). In-person study visits should attempt to coincide with routine standard of care office visits and relevant clinical data from such standard of care visits (including assessments for possible endpoint events or adverse events) will be collected and entered into the electronic case report form (eCRF). Standard of care (SOC) laboratory assessments as ordered by the primary nephrologist will be utilized. Iron status and serum phosphate collection and monitoring will be required as part of the SOC laboratory assessments. Laboratory assessments captured in the eCRF other than a screening pregnancy test for women of child-bearing potential and non-SOC iron and serum phosphorus labs, will utilize local laboratory results.

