#### **7.1.2 Dosing and Administration**

Study drug is not intended to be used as a treatment for either serum phosphorus or iron repletion. Management of serum phosphorus and iron sufficiency will be directed at the discretion of the treating physician and/or Investigator independent of study drug with the only restriction being that subjects cannot be prescribed commercial Auryxia (ferric citrate).

Subjects will be randomized in a 1:1 ratio to receive either ferric citrate or placebo. All subjects will be instructed to take study drug at a fixed dose of 2 tablets per meal or snacks, up to three times per day. The maximum dose is 6 tablets/day. No additional tablets (beyond a total of 6/day) should be taken. Tablets should not be crushed or chewed.

Every effort will be made to provide study drug to subjects at the Day 1 visit. If there are delays related to shipment from the USRC Rx pharmacy, study drug will be provided to subjects within 12 days of the Day 1 visit. Dosing will begin upon receipt of study drug with the next meal/snack. This would not be considered a protocol deviation.

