#### **7.1.2.1 Dose Adjustment**

No titration of study drug will be performed other than for issues of tolerability or safety.

It is expected that the Investigator will monitor serum phosphorus and iron indices per generally recognized standard of care for individuals with advanced CKD. The monitoring of iron indices

and serum phosphate is required at least every 3 months and failure to monitor these parameters will be considered a protocol deviation.

Required dose adjustments for low serum phosphorus are as follows:

- If serum phosphorus is  $<3.0$  mg/dL captured by a single value, the study drug, and any other prescribed phosphate lowering therapy, should be temporarily held until such time as serum phosphorus is  $\geq 3.0$  mg/dL at which time study drug may be resumed at a dose that is approximately equivalent to 50% of the previous total daily dose. The reduction in dose relative to meals or snacks is at the discretion of the investigator as long as it represents a total dose reduction of 50%. Repeat assessment of serum phosphorus will be at the discretion of the Investigator. This assessment must occur at the next scheduled visit (which may be up to three months), or it may also be performed earlier. Other prescribed phosphate lowering therapy may be resumed per investigator discretion when serum phosphorus is  $\geq 3.0$  mg/dL.

Required dose adjustments for high TSAT are as follows:

- If TSAT is  $>45\%$  and  $\leq 50\%$ , captured by a single laboratory value, the study drug should be reduced by 1 tablet per meal or snack (reduce the dose by the equivalent of 50%). Any other prescribed oral or IV iron therapy should be stopped.

If TSAT is  $>50\%$ , captured by a single laboratory value, the study drug, and any other prescribed oral or IV iron therapy, should be temporarily held until such time as TSAT is  $\leq 50\%$  (captured by a single laboratory value) at which time study drug may be resumed at a dose that is equivalent to 50% of the previous total daily dose. The reduction in dose relative to meals or snacks is at the discretion of the investigator as long as it represents a total dose reduction of 50%. Repeat assessment of iron indices will be at the discretion of the Investigator. This assessment must occur at the next scheduled visit (which may be up to three months), or it may also be performed earlier.

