### **7.5.3 Erythropoiesis-Stimulating Agents (ESAs) or Packed Red Blood Cell (PRBC) Transfusion**

There are no restrictions on the use of ESA and dose adjustments may be made at the discretion of the Investigator. All changes in ESA therapy will be captured in source documentation and in the eCRF

Receipt of RBC transfusions will be captured in source documentation and in the eCRF.

- Subjects who receive repeated red blood cell transfusions during the study may need to temporarily hold study drug. For the purpose of the study, “repeated blood transfusion” will be defined as receipt of >4 units of red blood cells within any 6-month period of time. Prior to study drug hold please contact the medical monitor. If study drug is permanently discontinued, subsequent study visits including the Follow Up visit (Visit 6) should occur per the SoA.

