## **8.0 DISCONTINUATION OF STUDY INTERVENTION AND PARTICIPANT DISCONTINUATION/WITHDRAWAL**

### **8.1 Discontinuation of Study Drug**

#### **8.1.1 Temporary Interruption of Study Drug**

Discontinuation from study drug is different from discontinuation from the study, and remaining study procedures will be completed as indicated by the study protocol. The Investigator is strongly encouraged to resume study drug as soon as the reason for temporary interruption is over. Reasons for temporary discontinuation of study drug include:

- Drug-related AEs per the Investigator's discretion
- Unforeseen circumstances per the Investigator's discretion
- Serum phosphorus <3.0 mg/dL
- TSAT is >50%
- Ferritin >500 ng/mL
- Repeated red blood cell transfusions (>4 units of red blood cells within any 6-month period of time). See Section 7.5.3.
- Significant elevation in liver enzymes (SGOT and/or SGPT) >3X ULN or pancreatic enzymes (amylase and/or lipase) >2X ULN or elevation in total bilirubin >2X ULN, without an identifiable alternate etiology. Study drug should not be resumed prior to discussion with Medical Monitor.

The study drug may be restarted when the reason for temporary discontinuation is resolved. If study drug is temporarily discontinued due to elevations in iron indices, both TSAT and ferritin laboratory values must be within protocol-defined ranges prior to resumption of study drug.

The data to be collected at the time of study drug discontinuation should be in accordance with the SoA.

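### SAP 3.2's 70% exposure rule states neither a time window nor how required drug holds count, and SAP 3.8 may reuse the same outcome-dependent percentage as a covariate

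*SAP*

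**What the plan says.** The per protocol (PP) set in SAP 3.2 consists of "full analysis subjects who received a non-zero dose of study medication at least 70% of their time in study", with no protocol deviations affecting the primary analysis. SAP 3.4.4 and 3.4.5 name it as the supportive population for the primary and all secondary endpoints. SAP 3.4.7 repeats the measure at 50%, 60% and 80%. SAP 3.8 says that the same percentage may be used as a covariate, in an mITT population that SAP 3.2 does not define. The PP definition in Protocol 10.2 has no exposure threshold.

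Protocol 7.1.2.1 and 8.1.1 call for a temporary hold when phosphorus is below 3.0 mg/dL, TSAT is above 50% or ferritin is above 500 ng/mL. On the recheck, 7.1.2.1 says: "This assessment must occur at the next scheduled visit (which may be up to three months), or it may also be performed earlier". Protocol 8.1.1 adds: "The Investigator is strongly encouraged to resume study drug as soon as the reason for temporary interruption is over". The transfusion hold in Protocol 7.5.3 is softer: "Subjects who receive repeated red blood cell transfusions during the study may need to temporarily hold study drug".

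Several statements bear on the clock, but none defines it:

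- SAP 2.1: "Treatment Period: Up to 9 months".
- SAP 3.3: "the 10-month follow-up safety visit date will be capped at 307 days post study drug Day 1".
- Protocol 1.3 allows ±30 days around the Month 9 end-of-treatment visit.
- Protocol 7.1.2: if shipment is delayed, "study drug will be provided to subjects within 12 days of the Day 1 visit".
- Protocol 5.1: subjects who start maintenance dialysis or receive a transplant "will be removed from study with no follow-up visit".

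**The concern.** The numerator counts days on a non-zero dose, and no exception is made for holds. A subject who does exactly what the protocol requires can therefore fall out of the per protocol set. Because the denominator has no stated start or end, whether some subjects are included depends on a choice left to the programmer. The event itself cuts the denominator, so the percentage is partly a function of the outcome. Selecting on it or adjusting for it can then move the hazard ratio (HR) with no change in the treatment effect. A supportive HR that differs from the primary one only because of how days are counted could be read as a lack of robustness.

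**Working it through.** **1. The plan's own figures.** The documents give no derivation for the 70% threshold. The illustrations below borrow the SAP 3.1 inputs: 0.94 events per person-year on control, 0.75 years of follow-up and HR 0.60. These reproduce the planned size. Event probabilities are 1 − exp(−0.94 × 0.75) = 0.506 and 1 − exp(−0.60 × 0.94 × 0.75) = 0.345. Freedman's formula gives (1.6/0.4)² × (1.960 + 1.282)² ≈ 168.1, so 169 events. N = 169 / [(0.506 + 0.345)/2] = 398, against the stated 400.

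**2. Day counts.** Score = days on a non-zero dose / days on the clock. The subject starts on Day 1 and is dosed to Day 270 apart from one hold.

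| Clock ends | 90-day hold | 60-day hold | Longest hold still at 70% |
|---|---|---|---|
| Day 270 | 180/270 = 66.7% | 210/270 = 77.8% | 270 − 189 = 81 days |
| Day 300 | 180/300 = 60.0% | 210/300 = 70.0% | 270 − 210 = 60 days |
| Day 307 | 180/307 = 58.6% | 210/307 = 68.4% | 270 − 214.9 = 55 days |

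A 60-day hold passes, sits exactly on the limit, or fails, depending on the unstated end. If end of treatment falls on Day 300, dosing continues until then and the clock stops there, a 90-day hold scores 210/300 = 70.0% and the subject is kept. The start matters too: with drug received 12 days late and a clock from Day 1, the 81-day allowance falls to 258 − 189 = 69 days.

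**3. Dependence on outcome.** Take a hold from Day 90, with drug resumed at Day 180 if the subject is still event-free.

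- Event at Day 100: 90/100 = 90.0%, kept.
- Event at Day 128: 90/128 = 70.3%, kept.
- Event at Day 129: 90/129 = 69.8%, excluded.
- Event-free to Day 270: 180/270 = 66.7%, excluded.

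**4. The SAP 3.8 covariate.** With no holds and a clock to Day 300, every subject with an event scores 100% and every event-free completer scores 270/300 = 90%, so the covariate simply encodes the outcome. In a simulation of 100,000 per arm (constant hazard, Cox model on treatment and the percentage), a true HR of 0.60 became 0.93. A true HR of 1.00 stayed at 1.00. A clock ending at Day 270 removes that artefact but not the whole problem: with 90-day holds at 20% (ferric citrate) vs 5% (placebo) per visit, a true 0.60 became 0.72.

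**5. The PP hazard ratio.** These are scenarios, not estimates. Assumptions: holds start at Day 90 and/or Day 180, are unrelated to prognosis, and leave the treatment effect unchanged; the Cox model is unadjusted. Rates are per visit, ferric citrate vs placebo.

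| Scenario | PP HR, truth 0.60 | PP HR, truth 1.00 |
|---|---|---|
| 20% vs 5%, 90 days, Day 270 clock | about 0.75 | about 1.2 |
| 10% vs 5%, 90 days, Day 270 clock | about 0.65 | 1.06 to 1.07 |
| 20% in both arms, 90 days, Day 270 clock | about 0.62 | 1.00 |
| 20% vs 5%, 60 or 80 days, Day 270 clock | 0.59 | 0.99 to 1.00 |
| 20% vs 5%, 60 days, Day 307 clock | 0.76 | 1.20 |
| No holds; 20% vs 5% of subjects with an event stop drug 60 days before it | 0.53 | 0.90 |

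The fourth and fifth rows show that the choice of clock alone can create or remove the bias. The last row shows that the direction can reverse.

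**The case against.** The strongest reply is that little depends on this. Efficacy rests on the full analysis set, PP is supportive, and SAP 3.8 is optional. That stands, and it sets the severity.

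The reply also says that the inputs are assumed. The documents give no hold rates, no hold lengths and no difference between arms. Three months is a maximum, and prompt resumption is encouraged. That stands as well, so the PP figures show a mechanism and no more. It does not answer the missing window or the 3.8 result, which needs no holds.

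Third, Day 270 is the natural end, and SAP 3.3 counts from study drug Day 1, which suggests a drug-start anchor. Both are reasonable readings, but SAP 3.2 states neither. SAP 3.3 caps dates for vital status and the Month 10 visit; it does not define this percentage.

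Fourth, the planned 50% and 60% subsets would expose the artefact. In the 20% vs 5%, 90-day scenario they give 0.62 and 0.60 at a true 0.60, while the 80% subset gives 0.74. This is partial protection.

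Fifth, the SAP measures exposure, and crediting holds changes that to adherence: a subject held from Day 90 to Day 270 would score 100%. This stands, so a hold-credited version should be added and should not replace the exposure-based set.

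A reader might infer that a 90-day hold excludes a completer on every reading; the ±30-day window at Month 9 shows otherwise. A reader might also take the adverse event rates in Protocol 3.3.1 (75.3% vs 61.7%) as evidence that holds will differ by arm. Those are overall treatment-emergent event rates and say nothing about laboratory holds.

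**Conclusion.** The definition is incomplete, and the percentage depends on outcome. Both follow from the text and simple arithmetic. If off-drug safety follow-up enters the denominator, the SAP 3.8 covariate distorts the HR even with no holds (0.60 to about 0.93 at 0.94 events per year, with follow-up for events to Day 270). This assumes that the percentage enters as one value per subject, which SAP 3.8 implies but does not spell out.

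The stronger reading, that required holds will bias the PP result against ferric citrate, is not supported. On a Day 270 clock, material bias needs holds longer than 81 days at different rates by arm, and drug stopped shortly before an event pushes the other way. The primary analysis and the sample size are untouched. Severity is minor, limited to supportive and optional analyses.

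**What to change.** (a) SAP 3.2, 3.4.7 and 3.8: use one exposure window, from first dose to the earliest of primary event, transplant, withdrawal or the actual end-of-treatment date, excluding safety follow-up and vital-status days. State that end of treatment means the Month 9 visit and not the last dose; otherwise an early stopper scores 100%.

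(b) SAP 3.8: drop the percent-of-time covariate, or use current exposure as a time-dependent variable. In a check with 8,000 per arm at a true 0.60, the time-dependent form gave 0.62 (90-day holds, 20% vs 5%, Day 270 clock). Replace mITT with the Full analysis population.

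(c) SAP 3.2: beside the exposure-based set, report a version in which days of protocol-required laboratory holds do not count against the subject, and show actual percent of days on drug by arm. Label the PP and 50/60/80% results as descriptive, because selection on post-baseline exposure remains. With assumed voluntary stopping of 0.5 vs 0.2 per year, a hold-credited PP HR is still 0.65 at a true 0.60.

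The cost is SAP wording, a little programming and one extra supportive table. No new data are needed, since Protocol 7.1.2.1 and 9.4 already put dose adjustments in the eCRF. No clinical hold rule changes.
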